**Type 2 (Imbalance between myocardial oxygen supply and demand)\***

- Detection of a rise and/or fall of cTn values with at least one value above the 99th percentile URL, and evidence of an imbalance between myocardial oxygen supply and demand unrelated to coronary thrombosis, requiring at least one of the following:
  - Symptoms of ischaemia
  - ECG changes indicative of new ischaemia (new ST-segment or T-wave changes or new LBBB)
  - New pathologic Q-waves in  $\geq 2$  contiguous leads
  - Imaging evidence of a new loss of viable myocardium or new wall motion abnormality

**Type 3 (MI associated with sudden cardiac death)\***

- Patients who suffer cardiac death, with symptoms suggestive of myocardial ischaemia accompanied by presumed new ischaemic ECG changes or ventricular fibrillation but die before blood samples for biomarkers can be obtained, or before increases in cardiac biomarkers can be identified, or MI is detected by autopsy examination.

**Type 4A (Criteria for PCI-related MI  $\leq 48$  h after the index procedure)†**

- **In patients with normal baseline CK-MB:** The peak CK-MB measured within 48 h of the procedure  $\geq 10 \times$  the local laboratory ULN or CK-MB  $\geq 5 \times$  ULN with one or more of the following:
  - New pathologic Q-waves in  $\geq 2$  contiguous leads
  - New persistent LBBB‡
  - Flow-limiting angiographic complications in a major epicardial vessel or  $>1.5$  mm diameter branch
  - Substantial new loss of viable myocardium on imaging related to the procedure
- In the absence of CK-MB measurements and a normal baseline cTn, a cTn (I or T) level measured within 48 h of the procedure rises to  $\geq 70 \times$  the local laboratory ULN or  $\geq 35 \times$  ULN with one or more of the following:
  - New pathologic Q-waves in  $\geq 2$  contiguous leads
  - New persistent LBBB‡
  - Flow-limiting angiographic complications in a major epicardial vessel or  $>1.5$  mm diameter branch
  - Substantial new loss of viable myocardium on imaging related to the procedure
- **In patients with elevated baseline CK-MB (or cTn):** The CK-MB (or cTn) rises by an absolute increment equal to those levels recommended above from the most recent pre-procedure level plus new ECG changes as described.

**Type 4B (Stent thrombosis)\***

- Stent thrombosis as documented by angiography or autopsy using the same criteria utilized for type 1 MI.
  - Acute: 0 to 24 h
  - Subacute:  $>24$  h to 30 days
  - Late:  $>30$  days to 1 year
  - Very late:  $>1$  year after stent implantation

**Type 4C (Coronary stent restenosis)\***

- Focal or diffuse restenosis, or a complex lesion associated with a rise and/or fall of cTn values above the 99th percentile URL applying, the same criteria utilized for type 1 MI

**Type 5 Peri-procedural (post-SAVR, TAVR or CABG) MI ( $\leq 48$  h after the index procedure)‡**

- **In patients with normal baseline CK-MB:** The peak CK-MB measured within 48 h of the procedure  $\geq 10 \times$  the local laboratory ULN or CK-MB  $\geq 5 \times$  ULN with one or more of the following:
  - New pathologic Q-waves in  $\geq 2$  contiguous leads
  - New persistent LBBB‡
  - Flow-limiting angiographic complications in a major epicardial vessel or  $>1.5$  mm diameter branch
  - Substantial new loss of viable myocardium on imaging related to the procedure
- In the absence of CK-MB measurements and a normal baseline cTn, a cTn (I or T) level measured within 48 h of the procedure rises to  $\geq 70 \times$  the local laboratory ULN or  $\geq 35 \times$  ULN with one or more of the following:
  - New pathologic Q-waves in  $\geq 2$  contiguous leads
  - New persistent LBBB‡
  - Flow-limiting angiographic complications in a major epicardial vessel or  $>1.5$  mm diameter branch
  - Substantial new loss of viable myocardium on imaging related to the procedure
- **In patients with elevated baseline CK-MB (or cTn):** The CK-MB (or cTn) rises by an absolute increment equal to those levels recommended above from the most recent pre-procedure level plus new ECG changes as described.

The use of high-sensitivity (hs)-troponins is recommended for diagnosis of spontaneous MI, but has not been studied for assessment of peri-procedural MI. Standard troponin assays are therefore recommended for evaluation of peri-procedural MI. Peri-procedural biomarker elevation  $>ULN$  not meeting the criteria for MI should be categorized as 'myocardial injury not meeting MI criteria'.

\*Adapted from Thygesen *et al.* (169).

†Adapted from Moussa *et al.* (167) and Garcia-Garcia *et al.* (168).

‡LBBB criteria to be used with caution after TAVR or SAVR given the relatively high rate of new LBBB after these procedures.

CK-MB = creatine kinase-MB; cTn, cardiac troponin; ECG = electrocardiogram; LBBB = left bundle branch block; MI, myocardial infarction; SAVR = surgical aortic valve replacement; TAVR = transcatheter aortic valve replacement; ULN = upper limit of normal; URL = upper reference limit.

## 8.17 Stroke (cerebrovascular accident)

**TABLE 3** Neurologic events

**Categories of neurologic events**

Overt CNS injury (NeuroARC Type 1)
 
All stroke*
 
 
■ Ischaemic stroke† Acute onset of focal neurological signs or symptoms conforming to a focal or multifocal vascular territory within the brain, spinal cord, or retina (NeuroARC Type 1a or 1aH) and fulfilling one of the following criteria:           
 
■ Signs or symptoms lasting <math>\geq 24</math> h or until death, with pathology or neuroimaging evidence of CNS infarction, or absence of other apparent causes
 
■ Symptoms lasting <math>< 24</math> h, with pathology or neuroimaging confirmation of CNS infarction in the corresponding vascular territory‡
 
 
 
■ Haemorrhagic stroke Acute onset of neurological signs or symptoms due to intracranial bleeding from intracerebral or subarachnoid haemorrhage not due to trauma (NeuroARC Types 1b or 1c)
 
■ Stroke, not otherwise specified Acute onset of neurological signs or symptoms persisting <math>\geq 24</math> h or until death but without sufficient neuroimaging or pathology evidence to be classified (NeuroARC Type 1d)
 
 
Symptomatic hypoxic-ischaemic injury Non-focal (global) neurological signs or symptoms with diffuse brain, spinal cord, or retinal cell death confirmed by pathology or neuroimaging and attributable to hypotension or hypoxia (NeuroARC Type 1e)

Covert CNS injury (NeuroARC Type 2)
 
Covert CNS infarction‡ or haemorrhage Neuroimaging or pathological evidence of CNS focal or multifocal ischaemia (NeuroARC Type 2a or 2aH) or haemorrhage (NeuroARC 2b) without acute neurological symptoms consistent with the lesion or bleeding location

Neurologic dysfunction (acutely symptomatic) without CNS injury (NeuroARC Type 3)
 
TIA Transient focal neurological signs or symptoms lasting <math>< 24</math> h presumed to be due to focal brain, spinal cord, or retinal ischaemia, but without evidence of acute infarction by neuroimaging or pathology, or with no imaging performed (NeuroARC Type 3a or Type 3aH)
 
Delirium without CNS injury Transient non-focal neurological signs or symptoms, typically of variable duration, without evidence of infarction on neuroimaging or pathology, or with no imaging performed (NeuroARC Type 3b)


Stroke grading*
 
Acute stroke severity§
 
 
■ Mild neurological dysfunction: NIHSS 0-5
 
■ Moderate neurological dysfunction: NIHSS 6-14
 
■ Severe neurological dysfunction: NIHSS <math>\geq 15</math>
 
 
Stroke disability  
 
 
■ Fatal Stroke: death resulting from a stroke
 
■ Stroke with disability: mRS score of <math>\geq 2</math> at 90 days   and increase of <math>\geq 1</math> from pre-stroke baseline
 
■ Stroke without disability: mRS score of 0 (no symptoms) or 1 (able to carry out all usual duties and activities) at 90 days   or no increase in mRS category from pre-stroke baseline
 

Neurological events timing
 
 
■ Periprocedural: Occurring <math>\leq 30</math> days after the index procedure           
 
■ Acute: Occurring <math>\leq 24</math> h after the index procedure
 
■ Sub-acute: Occurring <math>> 24</math> h and <math>\leq 30</math> days after the index procedure
 
 
 
■ Early: Occurring <math>> 30</math> days and <math>\leq 1</math> year after the index procedure
 
■ Late: Occurring <math>> 1</math> year after the index procedure
 

## 8.18 Bleeding complications

**TABLE 5** Bleeding and transfusions\*

Overt bleeding† that fulfils one of the following criteria:

**Type 1**

- Overt bleeding that does not require surgical or percutaneous intervention, but does require medical intervention by a health care professional, leading to hospitalization, an increased level of care, or medical evaluation (BARC 2)
- Overt bleeding that requires a transfusion of 1 unit of whole blood/red blood cells‡ (BARC 3a)

**Type 2**

- Overt bleeding that requires a transfusion of 2-4 units of whole blood/red blood cells‡ (BARC 3a)
- Overt bleeding associated with a haemoglobin drop of >3 g/dL (>1.86 mmol/L) but <5 g/d (<3.1 mmol/L) (BARC 3a)

**Type 3**

- Overt bleeding in a critical organ, such as intracranial, intraspinal, intraocular, pericardial (associated with haemodynamic compromise/tamponade and necessitating intervention), or intramuscular with compartment syndrome (BARC 3b, BARC 3c)
- Overt bleeding causing hypovolemic shock or severe hypotension (systolic blood pressure <90 mmHg lasting >30 min and not responding to volume resuscitation) or requiring vasopressors or surgery (BARC 3b)
- Overt bleeding requiring reoperation, surgical exploration, or re-intervention for the purpose of controlling bleeding (BARC 3b, BARC 4)
- Post-thoracotomy chest tube output ≥2 L within a 24-h period (BARC 4)
- Overt bleeding requiring a transfusion of ≥5 units of whole blood/red blood cells (BARC 3a) ‡
- Overt bleeding associated with a haemoglobin drop ≥5 g/dL (≥3.1 mmol/L) (BARC 3b).

**Type 4**

- Overt bleeding leading to death. Should be classified as:
  - **Probable:** Clinical suspicion (BARC 5a)
  - **Definite:** Confirmed by autopsy or imaging (BARC 5b)

For the current study, the bleeding complications 3a, 3b, 3c, 4, 5a and 5b will be considered.

## 8.19 Acute kidney injury

**TABLE 10** Acute kidney injury\*

**Stage 1**

AKI that fulfils at least one of the following criteria:

- Increase in serum creatinine ≥150-200% (≥1.5-2.0× increase) within 7 days compared with baseline
- Increase of ≥ 0.3mg/dL (≥26.4 μmol/L) within 48 h of the index procedure

**Stage 2**

AKI that fulfils the following criterion:

- Increase in serum creatinine >200-300% (>2.0-3.0× increase) within 7 days compared with baseline

**Stage 3**

AKI that fulfils at least one of the following criteria:

- Increase in serum creatinine >300% (>3.0× increase) within 7 days compared with baseline
- Serum creatinine ≥4.0 mg/dL (≥354 μmol/L) with an acute increase of ≥0.5 mg/dL (≥44 μmol/L)

**Stage 4**

AKI requiring new temporary or permanent renal replacement therapy

Adapted from Clinical Practice Guidelines for Acute Kidney Injury 2012. <https://kdigo.org/guidelines/acute-kidney-injury/>.

\*Given practical challenges with the use of urine output criteria in daily practice, AKI should be solely defined based on serum creatinine values. Acute kidney injury defined by urine output using the following criteria might be used in the context of a dedicated AKI study: AKI Stage 1: Urine output <0.5mL/kg/h for ≥6 but <12 h; AKI stage 2: Urine output <0.5mL/kg/h for ≥12 but <24h; AKI stage 3: Urine output <0.3mL/kg/h for ≥24 h or anuria for ≥12 h.

AKI = acute kidney injury.

## 8.20 Vascular access site and access-related complications

**TABLE 6** Vascular and access-related complications\*

Vascular complications†

Major

One of the following:

- Aortic dissection or aortic rupture
- Vascular (arterial or venous) injury (perforation, rupture, dissection, stenosis, ischaemia, arterial or venous thrombosis including pulmonary embolism, arteriovenous fistula, pseudoaneurysm, haematoma, retroperitoneal haematoma, infection) or compartment syndrome resulting in death, VARC type  $\geq 2$  bleeding, limb or visceral ischaemia, or irreversible neurologic impairment
- Distal embolization (non-cerebral) from a vascular source resulting in death, amputation, limb or visceral ischaemia, or irreversible end-organ damage
- Unplanned endovascular or surgical intervention resulting in death, VARC type  $\geq 2$  bleeding, limb or visceral ischaemia, or irreversible neurologic impairment
- Closure device failure‡ resulting in death, VARC type  $\geq 2$  bleeding, limb or visceral ischaemia, or irreversible neurologic impairment

Minor

One of the following:

- Vascular (arterial or venous) injury (perforation, rupture, dissection, stenosis, ischaemia, arterial or venous thrombosis including pulmonary embolism, arteriovenous fistula, pseudoaneurysm, haematoma, retroperitoneal haematoma, infection) *not* resulting in death, VARC type  $\geq 2$  bleeding, limb or visceral ischaemia, or irreversible neurologic impairment
- Distal embolization treated with embolectomy and/or thrombectomy, *not* resulting in death, amputation, limb or visceral ischaemia, or irreversible end-organ damage
- Any unplanned endovascular or surgical intervention, ultra-sound guided compression, or thrombin injection, *not* resulting in death, VARC type  $\geq 2$  bleeding, limb or visceral ischaemia, or irreversible neurologic impairment
- Closure device failure‡ *not* resulting in death, VARC type  $\geq 2$  bleeding, limb or visceral ischaemia, or irreversible neurologic impairment

Access-related non-vascular complications

Major

One of the following:

- Non-vascular structure, non-cardiac structure§ perforation, injury, or infection resulting in death, VARC type  $\geq 2$  bleeding, irreversible nerve injury or requiring unplanned surgery or percutaneous intervention
- Non-vascular access site (e.g. trans-apical left ventricular) perforation, injury, or infection resulting in death, VARC type  $\geq 2$  bleeding, irreversible nerve injury or requiring unplanned surgery or percutaneous intervention

Minor

One of the following:

- Non-vascular structure, non-cardiac structure§ perforation, injury, or infection *not* resulting in death, VARC type  $\geq 2$ , irreversible nerve injury, or requiring unplanned surgery or percutaneous intervention
- Non-vascular access site (e.g. trans-apical left ventricular) perforation, injury, or infection *not* resulting in death, VARC type  $\geq 2$  bleeding, irreversible nerve injury or requiring unplanned surgery or percutaneous intervention

## 8.21 Conduction disturbances and arrhythmias

**TABLE 9** Conduction disturbances and arrhythmias

### Pre-index procedure

- **Conduction disturbances**
  - 1st-degree AV block
  - 2nd-degree AV block
  - Left bundle branch block
  - Right bundle branch block
  - IVCD with QRS  $\geq$ 120 ms
  - Bradycardia (heart rate <60 b.p.m.) or SSS
- **Permanent pacemaker**
  - Type of permanent pacemaker should be recorded (e.g. single chamber, dual chamber, biventricular, defibrillator)
- **Atrial fibrillation (or flutter)**
  - Paroxysmal, persistent, long-standing persistent, or permanent

### During or after index procedure\*

- **Conduction disturbances**
  - 1st-, 2nd-, 3rd-degree AV block
  - Left bundle branch block
  - IVCD with QRS  $\geq$ 120 ms
  - **New-onset:** defined as a new conduction disturbance relative to baseline
  - **Timing of occurrence:** Procedural:  $\leq$ 24 h after the index procedure  
Delayed: >24 h after the index procedure
  - **Duration:** Transient: resolved before discharge or  $\leq$ 7 days after the index procedure in case of prolonged hospitalization  
Persistent: present at hospital discharge or >7 days after the index procedure in case of prolonged hospitalization  
Permanent: present >30 days after the index procedure
- **Permanent pacemaker**
  - **Type:** single, dual, biventricular, defibrillator, leadless
  - **Timing:** No. of days after the index procedure
  - **Indication:** including AV Block, SSS
- **Atrial fibrillation (or flutter)**
  - **New-onset:** defined as any arrhythmia that was not present at baseline that has the ECG characteristics of atrial fibrillation (or flutter) and lasts sufficiently long to be recorded on a 12-lead ECG or at least 30 s on a rhythm strip
  - **Timing of occurrence†:**  
Periprocedural:  $\leq$ 30 days after the index procedure  
Late/spontaneous: >30 days after the index procedure
  - **Duration†:**  
Paroxysmal: atrial fibrillation that terminates spontaneously or with intervention  $\leq$ 7 days of onset.  
Persistent: Continuous atrial fibrillation that is sustained >7 days.  
Long-standing persistent: Continuous atrial fibrillation >12 months in duration.  
Permanent: Used when the patient and clinician make a joint decision to stop further attempts to restore and/or maintain sinus rhythm.

\*The calculation of new pacemaker rates should exclude patients with pre-existing pacemaker. The same principle applies to reporting of rates of new conduction disturbances and arrhythmias.

†From January *et al* (136).

AF = atrial fibrillation or atrial flutter; AV = atrioventricular; ECG =, electrocardiogram; IVCD = intraventricular conduction delay; SSS = sick sinus syndrome.

## 8.22 Other TAVI-related complications

Table 9: Other TAVI-related complications

Conversion to open surgery
Conversion to open sternotomy during the TAVI procedure secondary to any procedure-related complications
Unplanned use of cardiopulmonary bypass (CPB)
Unplanned use of CPB for haemodynamic support at any time during the TAVI procedure
Coronary obstruction
Angiographic or echocardiographic evidence of a new, partial or complete, obstruction of a coronary ostium, either by the valve prosthesis itself, the native leaflets, calcifications, or dissection, occurring during or after the TAVI procedure
Ventricular septal perforation
Angiographic or echocardiographic evidence of a new septal perforation during or after the TAVI procedure
Mitral valve apparatus damage or dysfunction
Angiographic or echocardiographic evidence of new damage (chordae papillary muscle, or to the leaflet) to the mitral valve apparatus or dysfunction (e.g. restrictions due to the THV) of the mitral valve during or after the TAVI procedure
Cardiac tamponade
Evidence of a new pericardial effusion associated with haemodynamic instability and clearly related to the TAVI procedure
Endocarditis
Any one of the following
Fulfilment of the Duke endocarditis criteria a
Evidence of abscess, paravalvular leak, pus, or vegetation confirmed as secondary to infection by histological or bacteriological studies during a re-operation
Findings of abscess, pus, or vegetation involving a repaired or replaced valve during an autopsy
Valve thrombosis
Any thrombus attached to or near an implanted valve that occludes part of the blood flow path, interferes with valve function, or is sufficiently large to warrant treatment. Note that valve-associated thrombus identified at autopsy in a patient whose cause of death was not valve-related should not be reported as valve thrombosis
Valve malpositioning
Valve migration
After initial correct positioning, the valve prosthesis moves upwards or downwards, within the aortic annulus from its initial position, with or without consequences
Valve embolization
The valve prosthesis moves during or after deployment such that it loses contact with the aortic annulus
Ectopic valve deployment
Permanent deployment of the valve prosthesis in a location other than the aortic root
TAV-in-TAV deployment
An additional valve prosthesis is implanted within a previously implanted prosthesis because of suboptimal device position and/or function, during or after the index procedure

TAVI: transcatheter aortic valve implantation; THV: transcatheter heart valve.

aDurack *et al.* [72].

## 8.23 Quality of life

The quality of life will be assessed by 2 standardized and validated questionnaires:

- EuroQoL (EQ-5D)
- Kansas City Cardiomyopathy Questionnaire (KCCQ)-12

More detailed and comprehensive questionnaires are known to exist, but the ones above represent the best compromise between reliability and feasibility in the context of the present investigator-led study.

## 9 STATISTICAL ANALYSIS PLAN

All statistical analyses will be performed by an independent Statistical Committee. The analysis will be performed on an intention-to-treat (ITT) set, defined as all intentionally randomized patients, by randomization treatment. Supportive per-protocol analyses will be performed on the primary and key secondary endpoints. Correction for multiple testing to account for type I error will be performed according to Holm, and Bretz graphical approaches.

A detailed statistical analysis plan will be completed before the end of the study. In summary, continuous variables will be tested for normal distribution with the Kolmogorov-Smirnov test and with visual estimate of the QQ plot. Normally distributed variables will be presented as mean±SD and compared using the t test and one-way ANOVA. Otherwise, the median [inter-quartile range], Mann-Whitney U and Kruskal-Wallis tests will be used. Categorical variables will be summarized in terms of absolute and relative frequencies (percentages) and compared using  $\chi^2$  test. Statistical significance will be established at  $\alpha=0.05$  level. Formal type-I error control will be ensured for the primary and the secondary endpoint by correction for multiple testing according to Holm, and Bretz graphical approaches. Kaplan-Meier curves will be plotted to describe survival free from adverse events, and difference between groups will be tested with log-rank test. Further analyses will be performed setting as landmark the timing of TAVI procedure. Any confounding factor will be tested by Cox regression models. Variables with a p-value <0.1 in univariate analysis will be entered in a multivariate analysis to identify independent predictors. When appropriate, 95% CI will be calculated. In addition to the analysis of the first event, we will assess the primary composite outcome using the Finkelstein-Schoenfeld method, which is based on the principle that each patient in the clinical trial is compared with every other patient in a pairwise manner. The pairwise comparison proceeds in a hierarchical fashion, using all-cause mortality, followed by the frequency of hospital readmission when patients cannot be differentiated on the basis of mortality. This method gives a greater importance to all-cause mortality. We will apply the Finkelstein–Schoenfeld and the win ratio methods (Pocock et al, Eur Heart J 2012) to the patients stratified according to sex (male vs. female) and surgical risk (inoperable vs. other), yielding four stratification pools.

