### 4.2 Secondary efficacy endpoints

- All-cause death
- Cardiovascular death
- Myocardial infarction
- Hospital admission for cardiovascular cause
- Hospital admission for heart failure
- Cerebrovascular accident
- Ischemic stroke
- Hospital admission for pneumonia ( $\pm$  respiratory failure)
- Need for balloon aortic valvuloplasty for emergent condition
- Quality of life measured with the Eq-5D and KCCQ-12 scales
- Time spent on the waiting list before TAVI

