## 8.7 Study Heart Team: Indication to TAVI

The following information regarding each single patient will be analyzed and discussed:

- General medical history with major comorbidity (in particular: assessment of disease limiting life expectancy < 1 year; chronic kidney disease; severe peripheral artery disease)
- Medical therapy
- Frailty assessment (with geriatric assessment and estimation of overall quality of life)

- Concomitant cardiac conditions requiring intervention: coronary artery disease requiring revascularization; severe concomitant mitral or tricuspid regurgitation; severe septal hypertrophy; aortic aneurisms
  - Anatomical and procedural factors: TAVI feasible by transfemoral approach (or by other approaches); sequelae of chest radiation; porcelain aorta; high likelihood of severe patient prosthesis mismatch ( $AVA < 0.65 \text{ cm}^2/\text{m}^2$ ); severe chest deformation or scoliosis; aortic annular dimensions for the choice of TAVI valve (dimensions and model); aortic valve morphology (bicuspid aortic valve, severe calcification in left ventricle outflow-tract or of the leaflet); position of coronary ostia (to check for risk of coronary obstruction in case of low coronary ostia); presence of thrombus in aorta or in left ventricle.
- The decision to proceed with TAVI must be reached with consensus of the entire Study Heart Team for all patients.

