### Clinical efficacy (at 1 year and thereafter)

- Freedom from all-cause mortality
  - Freedom from all stroke
  - Freedom from hospitalization for procedure- or valve-related causes
  - Freedom from KCCQ Overall Summary Score <45 or decline from baseline of >10 point (i.e. Unfavourable Outcome)
-

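### Section 9's only rule for continuous outcomes is an unadjusted t test or Mann-Whitney comparison; for EQ-5D and KCCQ-12 this is valid but less precise than a baseline-adjusted analysis, and the readable text schedules no baseline score

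*Protocol*

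**What the plan says.** Section 4.2 of the protocol lists "Quality of life measured with the Eq-5D and KCCQ-12 scales" among eleven secondary efficacy endpoints, without a time point or a summary measure. Section 8.23 names the two instruments and gives no schedule.

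Section 9 describes how continuous variables will be handled. Normality is checked with a Kolmogorov-Smirnov test and a QQ plot. Then: "Normally distributed variables will be presented as mean±SD and compared using the t test and one-way ANOVA". For the rest: "Otherwise, the median [inter-quartile range], Mann-Whitney U and Kruskal-Wallis tests will be used". No covariate appears in either branch. The only covariate adjustment in the section is for time-to-event data: "Any confounding factor will be tested by Cox regression models". The section also announces that "A detailed statistical analysis plan will be completed before the end of the study" and presents these rules as a summary.

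Section 7.5 places quality of life at the visits after discharge (1, 6 and 12 months, then yearly to 3 years) and names EQ-5D alone. The assessment schedule in the synopsis lists inclusion and randomization as assessment points but ties no questionnaire to them. Figures in Sections 7.4 and 7.5 are not shown.

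Two other places touch on starting quality of life. The VARC-3 table reproduced in Section 8.10 includes a KCCQ criterion of "decline from baseline of >10 point". Section 8.7 asks the Heart Team for "Frailty assessment (with geriatric assessment and estimation of overall quality of life").

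**The concern.** A patient's score before treatment usually predicts the score afterwards. A two-sample comparison of follow-up scores leaves the predictable part in the error term, so the confidence interval is wider than it need be. Any chance difference in baseline scores between the arms also stays in the estimate in proportion to the correlation, and the control arm is the smaller one in this 2:1 trial. The eligible population runs from inoperable or frail patients to patients who qualify on age alone, so a wide spread of starting scores is plausible.

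The second part is more urgent. An analysis model can be chosen later, but a baseline score that was never collected cannot be recovered. The trial is open-label, so a questionnaire completed after the patient knows the allocated hospital is not a clean baseline. If neither instrument is scheduled at inclusion, no later analysis plan can adjust for baseline or apply a KCCQ criterion defined as a decline from it.

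**Working it through.** The protocol gives no precision or power figure for quality of life, so there is none to reproduce. The arm sizes come from the primary-endpoint calculation (Section 9.1: 187 control + 373 experimental = 560; 560 / 0.99 = 565.7, so 566) and are used here only as numbers analysed.

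**Inputs**
- From the protocol: n = 187 and 373; significance level 0.05, taken here as two-sided.
- Assumed, because the documents give no value: correlation r between baseline and follow-up score of 0.3, 0.5 or 0.7; equal SD in both arms and at both times; an illustrative true difference of 0.25 SD; and, for a second scenario, 80% of patients with a 1-year score.

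**Formulas, in units of the score's SD**
- Raw follow-up scores: SE = sqrt(1/n1 + 1/n2)
- Adjusted for baseline (ANCOVA): raw SE × sqrt(1 − r²)
- Change scores: raw SE × sqrt(2(1 − r))
- Power for difference d: Φ(d/SE − 1.96)

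**All 187/373 analysed.** Raw SE = sqrt(1/187 + 1/373) = sqrt(0.00803) = 0.0896.

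| r | Change-score SE | Adjusted SE | CI narrower than raw by | Equivalent raw N = 560/(1 − r²) | Power for 0.25 SD, raw | Power for 0.25 SD, adjusted |
|---|---|---|---|---|---|---|
| 0.3 | 0.1060 | 0.0855 | 4.6% | 615 | 79.7% | 83.3% |
| 0.5 | 0.0896 | 0.0776 | 13.4% | 747 | 79.7% | 89.6% |
| 0.7 | 0.0694 | 0.0640 | 28.6% | 1098 | 79.7% | 97.4% |

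Change scores do worse than raw scores at r = 0.3, equal them at r = 0.5 and do better at r = 0.7. They are less precise than the adjusted analysis at all three values.

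**80% with a score.** 0.8 × 187 ≈ 150 and 0.8 × 373 ≈ 298, so raw SE = sqrt(1/150 + 1/298) = 0.100. The difference detectable with 80% power is (1.96 + 0.8416) × 0.100 = 0.28 SD raw. Adjusted, it is 0.27, 0.24 and 0.20 SD at r = 0.3, 0.5 and 0.7. Power for 0.25 SD goes from 70% to 74%, 82% and 94%.

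**Chance imbalance.** Given an observed baseline difference, the raw estimate shifts by r times that difference. For an imbalance of one SE (0.0896 SD) the shift is 0.027, 0.045 and 0.063 SD at r = 0.3, 0.5 and 0.7. Averaged over randomizations the shift is zero.

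These figures describe a comparison of means. If a score fails the normality check, the stated Mann-Whitney test likewise makes no use of baseline.

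**The case against.** The strongest reply is that this belongs in the analysis plan. The rule is generic, is introduced as a summary, never mentions quality of life, and comes with a promise of a detailed plan, which is not shown. An adjusted model in that plan would be no surprise. This limits the point but does not remove it. The protocol does state a rule, the rule as worded reaches any continuous endpoint, and a later plan cannot supply a baseline that was not collected.

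Three stronger readings are tempting, and the documents do not support them:
- A reader might infer that quality of life is under formal type I error control. The sentence is "Formal type-I error control will be ensured for the primary and the secondary endpoint by correction for multiple testing", in the singular. Section 9 also mentions key secondary endpoints without listing them. Nothing names EQ-5D or KCCQ-12 as controlled.
- A reader might infer that raw follow-up scores are specified. The text is silent; a t test on change scores fits it equally well and would use baseline. At r = 0.7 the gain from ANCOVA over change scores is then modest: (0.0694/0.0640)² ≈ 1.18 in variance, against 1/(1 − 0.49) = 1.96 over raw scores.
- A reader might infer that the unadjusted estimate is biased. Under randomization it is not.

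The reply is also right that Section 5.5 stratifies by inoperable versus other, age below or from 85, sex, center and valve type, which limits imbalance in some sources of heterogeneity. It does not balance the scores themselves, and the stated tests do not use the strata. The supporting passages carry limited weight too: the VARC-3 KCCQ criterion is not part of this trial's primary endpoint, and the Heart Team's estimate is a clinical judgement, not a completed questionnaire. The unseen figures may already contain a baseline assessment.

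**Conclusion.** The point holds as one of efficiency and data collection for a secondary endpoint. The stated analysis is valid; a baseline-adjusted one is more precise for any r above zero. For assumed r of 0.3 to 0.7 the confidence interval would be about 5% to 29% narrower than with raw follow-up scores, and narrower than with change scores as well. The size depends on r, on which score is compared and on how many patients have a score, none of which the documents give. The direction does not depend on these.

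The readable text fixes no baseline for either instrument and no visit for KCCQ-12. If the figures that are not shown also lack them, the loss cannot be repaired for patients already randomized. The primary endpoint, the non-inferiority comparison and the sample size are unaffected.

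**What to change.** - **Section 9:** analyse EQ-5D and KCCQ-12 by ANCOVA, or a repeated-measures model, of the follow-up score adjusted for the baseline score. Report the adjusted mean difference with its 95% CI. Keep the t test/Mann-Whitney rule for descriptive comparisons.
- **Sections 7.5 and 8.23:** state that both questionnaires are completed at inclusion, before the allocation is disclosed, unless the schedule in the figures already says so, and that both are completed at the follow-up visits.

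The cost is a few sentences and, if no baseline is yet planned, one short completion of the two questionnaires at inclusion. If KCCQ-12 is not already in the visit schedule, its completion at follow-up has to be added, as the listed endpoint requires in any case. No extra patients are needed.
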